9.1.3 PK-PD Relationship Analysis

If appropriate, an exploratory analysis of the relationship between HMI-115 plasma concentration and pelvic pain score measured by NRS (cyclic, non-cyclic, and average) will be performed. The C_{trough} data will be represented graphically against pelvic pain scores (absolute and relative (expressed as %) change from baseline) and values of Prolactin by treatment.

9.2 Immunogenicity

Anti-drug antibodies will be measured using a three-tiered assay approach: screening assay, confirmatory assay and titration assay. Based on results using confirmatory assay, incidence of ADA will be summarized by visit on the immunogenicity analysis set. A shift table from baseline (positive/negative) to each scheduled post-baseline visit will be provided as well.

Samples confirmed as positive within the confirmatory assay, will be further evaluated in a neutralizing assay (NADA), so the by-visit summary of NADA (positive/negative) will also be provided on the Immunogenicity analysis set in all subjects with at least one ADA positive result. Percentage will be calculated for subjects with positive ADA at that visit.

All ADA and NADA data will be listed on the immunogenicity analysis set.

9.3 PGIC

The number and percentage of subjects in each PGIC response category (7-point scale) will be summarized at each visit including Week 5, Week 9, Week 13 and Week 25 for treatment group. The percentage of subjects with response of "Much Improved" or "Very Much Improved" will be combined and labeled as "Much Improved or Better". The remaining five categories of the PGIC scale will be combined and labeled "Other". The number and percentage of subjects with response of a) "Much Improved or Better" and b) "Other" will be summarized at each visit by treatment group, and comparison will be made between each HMI-115 treatment group and placebo group using a chi-square test, if the counts of equal or more than 20% cells are less than 5, the comparison will use Fisher exact test. In addition, the scores of PGIC will be summarized as continuous data to calculate means of each treatment group.

Score	Response category	Pooled category
1	Very much improved (better outcome)	Much Improved or Better (PGIC Responder)
2	Much improved	
3	Minimally improved	
4	No change	
5	Minimally worse	Other (PGIC Non-responder)
6	Much worse	
7	Very much worse (worse outcome)	

Statistical comparisons between each HMI-115 treatment group and placebo group in score (ranging 1 to 7) at each visit will be performed using ANOVA with treatment group and the randomization stratification factor of region as the fixed effects. If a subject has at least 15% increase of rescue medication use or changed to Opioids/Opioids+NSAIDs from NSAIDs at a particular visit (referring to Appendices Table 12.2) compared to baseline, such subjects will be considered as non-responders ('No change' category which the value will be set as 4) in the PGIC responder analysis for that visit.

PGIC data will be listed by subject and visit.

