9.3.1 Variables for Stratification of Randomization

This study employs a stratified randomization with two stratification factors: 1) region 2) participation in the intensive PK sampling subset (Yes, No). These stratification factors will be taken into account in the statistical analyses.

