9.4.9 Exploratory Analyses

Quality of life:

Quality of Life will be assessed with the HRQoL (Endometriosis Health Profile-5 [EHP-5]). EHP-5 data will be summarized descriptively by treatment group at each visit and will be compared using the MMRM and ANCOVA methods as used in for the primary endpoint.

PGIC:

The number and percentage of subjects in each PGIC response category will be summarized at each visit by treatment group. Statistical comparisons between each HMI-115 treatment group and placebo group in mean scores at each visit will be performed using ANOVA with treatment group as the fixed effect.

The percentage of subjects with response of "Much Improved" or "Very Much Improved" will be summarized at each visit by treatment group, and comparison will be made between each HMI-115 treatment group and placebo group using a chi-square test.

PK analysis:

The following parameters will be calculated for the extensive PK subset and will be reported in the clinical study report together with listing of sparse sampling:

- C_{max} , $C_{through}$, t_{max} , $AUC_{(0-tau)}$, $t_{1/2}$ following last dose
- AR for both C_{max} and AUC

Phoenix[®] WinNonlin[®] Version 8.2 or later will be used to calculate PK parameters using non-compartmental model according to the actual blood collection time.

The descriptive statistics of plasma concentrations will be made based on scheduled sampling time, and individual, average and median concentration-time curves will be separately plotted. PK parameters (extensive PK subset) will be summarized in descriptive statistics (mean, median, SD, minimum and maximum, coefficient of variation [CV%], geometric mean [GM] and geometric coefficient of variation [gCV%]).

A population pharmacokinetic (popPK) model might be developed using all available PK data. The data analysis plan will be described in a separate document from the SAP, and the results will be reported separately from the clinical study report.

PK-PD relationship:

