1.5 Randomization

All subjects will be centrally randomized using an Interactive Response Technology (IRT). The randomization will be stratified with two stratification factors 1) region and 2) participation in the intensive PK sampling subset. Each subject will be assigned a unique number (randomization number) that encodes the subject's assignment to different arms of the study.

Eligible subjects will be randomized into four arms: placebo, 60 mg, 120 mg, and 240 mg HMI-115 in a 1:1:1:1 ratio with 38 subjects/arm.

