7.1.2 Adjustments for Covariates

The primary efficacy analysis will be adjusted for the following covariates:

- Region (stratification variable): China, the USA and Europe
- Baseline measure of DYS measured by NRS

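### The PGIC responder test ignores region, although randomisation was stratified by it; a region-stratified test would be a cheap, minor improvement to an exploratory comparison

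*SAP*

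**What the plan says.** SAP 9.3 dichotomises the seven-point PGIC at each visit. For the responder proportion, "comparison will be made between each HMI-115 treatment group and placebo group using a chi-square test"; the sparse-data rule is that "if the counts of equal or more than 20% cells are less than 5, the comparison will use Fisher exact test". Both are tests on a single 2x2 table, with no stratification. No between-arm difference in proportions and no confidence interval is specified.

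For the PGIC score at the same visits, the same section specifies an "ANOVA with treatment group and the randomization stratification factor of region as the fixed effects".

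On design, SAP 1.5 states: "The randomization will be stratified with two stratification factors 1) region and 2) participation in the intensive PK sampling subset". SAP 7.1.2 lists the levels: "Region (stratification variable): China, the USA and Europe". Protocol 9.3.1 says of both factors: "These stratification factors will be taken into account in the statistical analyses".

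Protocol 9.4.9 also names a chi-square test for responders. For the score it had the comparison with "placebo group in mean scores at each visit will be performed using ANOVA with treatment group as the fixed effect". The SAP therefore added region to the score analysis and a Fisher fallback to the responder test, but did not bring region into the latter.

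**The concern.** One questionnaire is analysed in two ways at the same visits, once adjusted for region and once not, and no reason is given. The other planned dose-versus-placebo efficacy models (the primary ANCOVA, the pain secondaries, the rescue-medication ANCOVA and EHP-5) carry region. The exception is the subgroup analysis in SAP 7.1.6, where region defines the subgroup.

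The statistical reason to care is this. When randomisation balances the arms within region, between-region differences in response rate cannot move the arm contrast. The pooled 2x2 variance still counts them. The test then uses a standard error that is too large: it rejects too rarely under the null and misses some real differences. How much depends on how strongly region predicts PGIC response. At stake is the precision of an exploratory comparison.

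**Working it through.** **Inputs from the documents.** Randomised 1:1:1:1 with 38 per arm; 34 evaluable per arm (SAP 1.4); three regions; two-sided 5% with no multiplicity adjustment.

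**The plan's own figure.** There is no rate, effect or power statement for PGIC. The figures of 34 and 38 come from the DYS NRS calculation, which reproduces. With 34 per group, a 1-point change and SD 2.0, the paired t-test has 80.8% power (stated 80%), and 34/(1 - 0.10) = 37.8, so 38. They are used here only as plausible sample sizes.

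**Inputs that must be assumed.** Regional responder rates, region sizes and the treatment effect are not in the documents. Two sets were tried.

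**Set A: three equal regions, 34 per arm, response 30 points higher on active in every region.** The ratio of the correct standard error to the pooled one, under the null, is

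ratio = sqrt( mean of p(1-p) within regions / overall p(1-p) ), and the large-sample size of the chi-square is 2 x (1 - Phi(1.96/ratio)).

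- 30/40/50%: mean within = (0.21 + 0.24 + 0.25)/3 = 0.2333; overall = 0.40 x 0.60 = 0.24; ratio = sqrt(0.972) = 0.986.
- 20/40/60%: (0.16 + 0.24 + 0.24)/3 = 0.2133; ratio = sqrt(0.889) = 0.943; size about 4%.
- 15/40/65%: (0.1275 + 0.24 + 0.2275)/3 = 0.1983; ratio = sqrt(0.826) = 0.909; size about 3%.

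Simulation with 20,000 trials and regions balanced between arms:

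| Regional rates | Size, chi-square / CMH | Power, chi-square / CMH | Loss |
|---|---|---|---|
| 30/40/50% | 5.1 / 5.1% | 70 / 72% | 2 |
| 20/40/60% | 4.0 / 5.0% | 72 / 78% | 6 |
| 15/40/65% | 3.2 / 4.7% | 71 / 80% | 9 |

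**Set B: regions split about 50/26/24%, placebo response about 30% and active about 62% overall, common odds ratio, arms balanced by region.**

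| Placebo rates | Size of chi-square, n=34 | Power at 34, chi-square / CMH | Power at 38, chi-square / CMH |
|---|---|---|---|
| 30/30/30% | 5.4% | 75.7 / 75.4% | 81.0 / 81.0% |
| 25/35/35% | 5.4% | 75.7 / 76.1% | 81.4 / 81.5% |
| 20/40/40% | 4.8% | 76.1 / 78.8% | 82.4 / 83.1% |
| 15/45/45% | 4.2% | 77.2 / 82.4% | 82.9 / 85.5% |
| 10/50/50% | 3.2% | 78.1 / 86.2% | 84.2 / 89.8% |

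At 34 per arm the loss is therefore about 0, 0.4, 2.7, 5.2 and 8.1 points. At 38 it is 0, 0.1, 0.7, 2.6 and 5.6. CMH size stays between 4.8 and 5.1%. With the Fisher fallback (read as any observed cell below 5), the size at 34 per arm is 5.1, 5.1, 4.4, 3.9 and 2.9%, and power is unchanged.

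**If regional balance is lost** (Set B, region shares varying freely between arms), the chi-square is no longer conservative: its size is 5.1 to 5.6% in every scenario. At 15/45/45%, CMH still gains 80.4 - 75.5 = 4.9 points at 34 per arm and 84.8 - 81.2 = 3.6 at 38. With no region effect, CMH gives 80.4% against 81.6% at 38 per arm, a loss of 1.2 points.

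**The case against.** The strongest reply has four parts.

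- **No breach.** The specific PGIC text in Protocol 9.4.9 prescribes a chi-square test, and the SAP follows it. SAP 7.1.1 promises region adjustment for the primary variable and, where possible, the secondary ones; PGIC is exploratory. This largely stands. Protocol 9.3.1 is one general sentence, and the intensive-PK factor is also absent from the primary ANCOVA. What remains is an unexplained inconsistency within SAP 9.3.
- **Conservatism is not established.** A reader might infer that the planned test is conservative and loses power as a matter of fact. The documents do not support that, because they give no PGIC rates by region. Balance is not secured either. SAP 9.3 names no analysis set. If the general efficacy rule applies, the set is the surgically diagnosed PAS, and surgical diagnosis is not a stratification factor. Missing PGIC data can disturb balance further. This stands, and the claim must be conditional.
- **Stratifying is not free.** With little or no region effect, CMH can be weaker, by 1.2 points in the check above and by up to about 2 points under other assumptions. This stands, but the amount is small.
- **The stakes are low.** There is no power statement for PGIC, and a region-adjusted PGIC score comparison is already planned at every visit. This stands too. A reader might also infer that the meaningful-change threshold is affected, since PGIC is its anchor. It is not: the ROC analysis in SAP 7.2.5 relates individual PGIC responses to DYS change and never uses this between-arm test.

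**Conclusion.** The point holds as a minor, conditional improvement. The responder comparison ignores a factor that the randomisation used and that the adjacent score analysis includes. If regional responder rates differ, the unstratified test can lose power. With balanced arms and 34 per arm, the loss is about 0 to 3 points for regional spreads up to 20 percentage points and about 5 to 9 points for spreads of 30 to 50. At 38 per arm it is smaller: 2.6 points at a spread of 30 and 5.6 at 40. All of these rest on assumed regional rates, region sizes and effects.

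The chi-square test is valid as planned. Its size was never above 5.6% in the tabulated checks, so there is no material type I error inflation. Conservatism appears only when region is clearly prognostic and the arms are balanced by region. No primary or secondary conclusion changes, and the ROC threshold is untouched.

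**What to change.** In SAP 9.3, make the responder comparison of each dose with placebo a Cochran-Mantel-Haenszel test stratified by region (China, USA, Europe). Report a Mantel-Haenszel risk difference with 95% CI for each dose, which also supplies the between-arm estimate that the section now lacks. Use the exact stratified test when counts are sparse, and restate the sparseness trigger, because the present cell-count rule is written for a single 2x2 table. Keep the chi-square/Fisher result as supportive, since Protocol 9.4.9 names the chi-square. Name the analysis set for PGIC in the same edit.

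The cost is a sentence or two in the SAP and a small change to the SAS FREQ call. No new data are needed. The statistical price is up to about 1 to 2 points of power if region turns out to matter little. If the sponsor prefers the unstratified test, one sentence explaining why it differs from the score analysis would be enough.

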8.1.2 Evaluation of the need for Rescue Medication

Subjects will be supplied rescue pain medication (as listed in Table 6-3) that should be used only for endometriosis-associated pain throughout the study duration. Assessment will be based on the average number of rescue medication consumed by the subject and the percentage of days the subject took rescue medication.

Version 6.0 50 of 138 April 11, 2024

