The use of rescue medication will be taken into account in the analysis of the primary endpoints. In the ANCOVA analysis, if a subject has at least 15% increase of rescue medication use (in terms of medication counts) compared to baseline in the EOT menstrual cycle, the measurement for Week 12 will be imputed with the baseline NRS measurement (i.e. assuming no improvement from baseline). In the MMRM analysis, if a subject has at least 15% increase of rescue medication use at a particular visit compared to baseline, the measurement at that visit will be imputed with the baseline NRS measurement. Such subjects will also be considered non-responders in the PGIC responder analysis for that visit. The visit window for the MMRM analysis will be defined in the SAP.

In addition to rescue medications, all analgesic medications taken to treat pain other than endometriosis-associated pain will be captured as concomitant medications. The pain intensity NRS measurement for endometriosis-associated pain in the days when these concomitant pain medications are used will be considered unevaluable and will be imputed by the corresponding average baseline measurement (i.e. assuming no improvement from baseline on those days).

To study the dose-response relationship, the CFB to Week 12 will be plotted versus dose. A simple linear regression model will be fitted as a function of dose to characterize the dose-response relationship. In case of lack-of-fit of the simple linear regression model, multivariate or non-linear regression models may be explored.

Version 6.0 65 of 138 April 11, 2024

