The average pill count for any rescue analgesic use will be calculated by adding up the number of pills (NSAID and/or opioids) at a particular visit time frame and dividing by the actual number of days in the window with non-missing data from the corresponding menstruation cycle.

The pill count will be calculated as follows:

- Tier 1:
NSAID: 1 pill 200mg Naproxen (220mg Naproxen sodium) = 1 pill 200mg Ibuprofen
= 1 pill 25mg Diclofenac = 4 pills 50mg Celecoxib = 1 pill of NSAID use;
- Tier 2:
Opioids: the pill count for hydrocodone + acetaminophen, codeine phosphate + acetaminophen and tramadol + acetaminophen will be collected from eCOA directly.

First, rescue analgesic use should be categorized as Tier 1 or Tier 2. Then calculating the pill count in each Tier.

If the strength is not the same as the above strength, the pills count can be calculated by (actual strength per pill ÷ standard strength above) *number of pills taken in the last 24 hours for Tier 1.

Tier 1 and Tier 2 are not convertible to each other.

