7.2.2 Main Analytical Approach

The following approach (details are provided further down) is to be applied:

1. For subjects who **received at least 15% increase** in average pill count of rescue analgesic medications (**categorized as Non-Responder** per Table 7.1) OR upgraded from Tier 1 to Tier 2 or Tier 1+Tier 2 compared to Baseline measurement cycle, the change from baseline (CFB) in means of DYS measured by NRS at Week 6 measurement and/or Week 12 measurement will be handled per the following two scenarios:
 - a. If **CFB ≥ 0** , the CFB will be kept as it is.
 - b. If **CFB < 0** , the CFB will be **set to Zero**.
2. **Any missing** mean changes in DYS measured by NRS at Week 6 and/or Week 12 are **multiple imputed using a MAR approach**.
3. Any (observed or imputed) mean changes in DYS measured by NRS at Week 6 measurement and/or Week 12 measurement **after premature withdrawal** from study treatment (one of ICEs) is **set to missing and then multiple imputed using a missing-not-at-random (MNAR) approach**.

Multiple Imputation (MI) Approach

In the MI approach, the mean changes in DYS measured by NRS are multiple imputed: plausible values obtained from a prediction model applying first a MAR approach, followed by a specific MNAR approach applied for hypothetical strategy for handling the specific ICE.

As a monotone missing pattern cannot be expected, the fully conditional specification (FCS) method is used for dealing with arbitrary non-monotone missing data patterns. FCS is based on an iterative algorithm; at each iteration and for each variable of the prediction model, there is a prediction step and an imputation step. When missing values for the last variable in the sequence have been imputed, the algorithm cycles again through each variable, repeating the chain of regression estimation and imputation draw steps.

The full MI approach comprises of 4 steps:

- **Prediction Step:** current (iteration) values of the observed and imputed values are used to derive the predictive distribution for missing values under MAR, under MNAR mechanism also a function of the selected subset of observations (premature withdrawal from study treatment).
- **Imputation Step:** updated imputations are generated by draws from the predictive distribution defined by the updated regression model (prediction and imputation are done simultaneously by SAS Proc MI).

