12.2 Analysis Visit Window for Daily Assessment

Table 12.2: Analysis Visit Window for Scheduled Visit

Study Analysis Visit	Target Study Day	Time Interval (Study Day)	
		Start	End
Screening V1			
Screening V2			-1
Baseline		-35	-1
Week 1	Day 1	1	8
Week 3	Day 15	9	22
Week 5	Day 29	23	36
Week 7	Day 43	37	50
Week 9	Day 57	51	64
Week 11	Day 71	65	78
Week 13/EOT	Day 85	79	127
Week 25/FU	Day 169	≥128	

EOT=end of treatment; FU=follow-up.

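### SAP 9.3 judges PGIC response on rescue use in the Table 12.2 calendar windows instead of whole menstrual cycles; most of the Week 13 window falls after the rating it can overturn

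*SAP*

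**What the plan says.** The rule in SAP 9.3 begins "If a subject has at least 15% increase of rescue medication use or changed to Opioids/Opioids+NSAIDs from NSAIDs" and continues "at a particular visit (referring to Appendices Table 12.2) compared to baseline, such subjects will be considered as non-responders". The woman's score is then set to 4 (no change) in the responder analysis for that visit. PGIC is summarized at Weeks 5, 9, 13 and 25, and each dose is compared with placebo by chi-square or Fisher test.

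Table 12.2, headed "Analysis Visit Window for Daily Assessment", gives these windows: Baseline, Days -35 to -1; Week 5, Days 23 to 36; Week 9, Days 51 to 64; Week 13, Days 79 to 127 (target Day 85); Week 25, from Day 128 with no end day.

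Other sections measure rescue use differently:
- SAP 7.2.1 adds up pills and gets an average by "dividing by the actual number of days in the window with non-missing data from the corresponding menstruation cycle".
- SAP 7.2.2, step 1, applies the 15% rule to the average pill count "compared to Baseline measurement cycle".
- SAP 7.3.5 summarizes rescue use over the same cycle windows.
- Protocol 9.4.3 and the estimand table in SAP 7.2.1 also state the 15% rule as an average pill count. Protocol 8.1.2 says "Assessment will be based on the average number of rescue medication consumed by the subject".
- Protocol 9.4.4 is worded as "at least 15% increase of rescue medication use (in terms of medication counts) compared to baseline in the EOT menstrual cycle". It extends the rule to PGIC at each visit and adds that "The visit window for the MMRM analysis will be defined in the SAP".

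**The concern.** A PGIC rating given at a visit looks back over the time since treatment started (Protocol 10.7). A rescue override should therefore use diary days up to about that visit, and should compare like with like. The Table 12.2 windows do neither. The Week 13 window runs far into follow-up. The 14-day windows at Weeks 5 and 9 cover part of a cycle, and Day 1 is timed to cycle days 1 to 5 (Protocol 1.3, note 3), so a whole menses often falls inside them.

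At stake is the responder status of women who rate themselves 1 or 2; nobody else can change status. A woman who reports being much improved, and whose use has not risen, could be counted as a non-responder because of where the window falls. Because SAP 9.3 gives no unit, two programmers could also build different responder tables from the same diary data.

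**Working it through.** The plan gives no figure to reproduce, so the check is a day count from Table 12.2.

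**Window lengths** (end - start + 1): Baseline 35; Week 5, 36 - 23 + 1 = 14; Week 9, 64 - 51 + 1 = 14; Week 13, 127 - 79 + 1 = 49. Week 25 has no end day; it is 35, 42 or 49 days long if it stops at Day 162, 169 or 176.

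**1. Week 13 timing.** Days after the Day 85 rating: 127 - 85 = 42, and 42/49 = 86%. With the visit moved by 4 days either way (Protocol 1.3, note 4), 38 to 46 days follow it. The last dose is on Day 71, so the window ends 127 - 71 = 56 days after it, as Protocol Table 1-2 confirms for Day 127. This holds whatever unit is used.

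**2. Weeks 5 and 9, daily average.** Let r be daily use in menses divided by daily use outside it, m the menses days in the visit window and b the menses days in the baseline window. With unchanged use:

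ratio = [(14 + (r - 1)m)/14] / [(35 + (r - 1)b)/35], flagged if at least 1.15.

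Example: 28-day cycle, 5-day menses, Day 1 on cycle day k. Then m = 5 at both visits and b = 5 + (k - 1).
- r = 2, k = 1: (19/14)/(40/35) = 1.19, flagged.
- r = 2, k = 3: (19/14)/(42/35) = 1.13, not flagged.
- r = 2, k = 5: (19/14)/(44/35) = 1.08, not flagged.
- r = 3, k = 1 to 5: 1.33, 1.28, 1.22, 1.18, 1.13.
- r = 1.5: at most 1.10.

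Full grid: cycle length 21 to 35 days (Protocol 5.1, criterion 6), menses 3 to 7 days (assumption), k = 1 to 5 with k no greater than the menses length. That is 330 patterns. Share in which unchanged use is flagged:

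| r (assumed) | Week 5 | Week 9 | Week 13 |
|---|---|---|---|
| 1.5 or less | 0% | 0% | 0% |
| 2 | 32% | 15% | 0% |
| 3 | 68% | 32% | 1% |
| 4 | 79% | 40% | 5% |
| menses only | 85% | 45% | 28% |

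The largest ratio at r = 2 is 1.25. Since 1.15/1.25 = 0.92, a true fall of just over 8% clears every pattern. At r = 3, a 10% fall still leaves 21% flagged at Week 5 and 10% at Week 9.

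**3. Raw counts, if a programmer used them.** With even daily use: 14/35 = 0.40 at Weeks 5 and 9, so use must rise 1.15/0.40 = 2.9-fold before it is flagged. At Week 13, 49/35 = 1.40, so unchanged use is flagged unless it falls by about 18% (1.15/1.40 = 0.82).

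**Whole cycles instead.** For a regular cycle, unchanged use gives a ratio of 1.00 by construction. A simulation of 6,000 women per ratio (cycle length normal with mean 28 and SD 3, truncated to 21 to 35 days, with 2-day jitter) flagged 0% at every visit for r = 1 to 4, and 2.0 to 2.4% for menses-only use.

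**The case against.** **The count reading.** A reader might infer that the rule turns every woman with unchanged use into a Week 13 non-responder and hides even a doubling at Weeks 5 and 9. That needs raw counts, and the documents point the other way. Protocol 9.4.3, the SAP 7.2.1 estimand table and SAP 7.2.2 all put the 15% rule on an average pill count. The opioid limb of SAP 9.3 echoes 7.2.2, so 9.3 reads as shorthand for that rule. The count wording in Protocol 9.4.4 may only name pills as the unit. What stands is that SAP 9.3 should say so.

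**Calendar windows are allowed.** Protocol 9.4.4 leaves visit windows to the SAP. That is correct, so this is not a breach of the protocol. It does not justify a Week 13 window that lies mostly after the rating, or comparing part-cycles with 35 days. The table and listing shells may hold a fuller derivation, but they are not among the documents reviewed.

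**The cycle-phase error depends on an assumed ratio.** This also stands. The documents give no ratio, and entry requires non-menstrual pain as well (Protocol 5.1, criterion 3), so menses-only use is an extreme case.

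**A cycle-based rule fails when there is no menses.** This is fair: absent bleeding for 56 days is an event of special interest (Protocol 10.3.1). The fix needs a fallback.

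**Conclusion.** The point holds, at low priority. The Week 13 timing fault needs no assumption: 86% of the window follows the rating. The fault at Weeks 5 and 9 appears only if daily use in menses is about twice that outside it or more; at 1.5:1 or less there is none. The grid shares count regular-cycle patterns equally. They do not estimate how many women would be affected, and because many women rating 1 or 2 may have cut their use, the unchanged-use shares are upper figures.

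A reader might also infer a biased treatment comparison. The documents do not support that. The rule is the same in every arm, and its effect on the contrast cannot be computed from them. If an equal share f of women rating 1 or 2 were flagged in all arms, the responder-rate difference would shrink by the factor (1 - f), but f is unknown. PGIC is exploratory, the primary dysmenorrhea analysis uses cycle windows, and the Week 13 PGIC anchor in the ROC analysis (SAP 7.2.5) states no rescue override.

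**What to change.** In SAP 9.3, replace the reference to Table 12.2 with: average pills per day (7.2.1) over the menstrual cycle assigned to that visit, compared with the 7.2.1 baseline menstrual cycle. Assign cycles as follows:
- Weeks 5 and 9: a nearest-cycle rule modelled on the Week 6 rule in 7.2.1.
- Week 13: the EOT cycle.
- Week 25: the EOS cycle (7.3.1).
- No usable menses at a visit: average pills per day over a fixed calendar window ending at the visit, compared with Days -35 to -1. State the length of that window; 28 days, for example, would cover Days 2 to 29 at Week 5.

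If the calendar windows are kept, state average pills per day and name the Days -35 to -1 row as baseline. This settles the unit but leaves both window faults.

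Cost: two new cycle-window definitions, the fallback and some programming. The baseline, EOT and EOS cycles are already derived, and no new data are needed. Limits: on the grid, the nearest cycle can still end up to 13, 20 and 19 days after the Week 5, 9 and 13 visits (against 42 days for the present Week 13 window), and Weeks 9 and 13 share one cycle in 47 of 330 patterns (14%).
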